6.4 Efficacy

The following assessments of efficacy will be performed:

- Spirometry
- Health Status (PROs)
- e-Diary
- Peak Expiratory Flow
- Rescue Medication Use
- Asthma Exacerbations

6.4.1 Spirometry

The following spirometric assessments will be made:

- Forced expiratory volume in one second (FEV₁)
- Forced Vital Capacity (FVC)
- Forced Expiratory Flow between 25% and 75% of Forced Vital Capacity (FEF₂₅₋₇₅)

Spirometric assessments will be measured at Visit 201/202, 204, 207, 214 and EOT (if applicable) as indicated in [Table 6-2](#).

Trough FEV₁ is defined as the mean of the two FEV₁ values measured at 23 hr 15 min and 23 hr 45 min after the evening dose taken at the site.

Pre-dose FEV₁ is defined as the mean of the two FEV₁ values measured at -45 min and -15 min prior to evening dose.

Please refer to the Spirometry Guidance in [Appendix 4](#) and [Table 6-2](#) for full details on scheduling and performing spirometry.

6.4.2 Health Status (Patient Reported Outcomes)

6.4.2.1 Asthma Control Questionnaire (ACQ-7)

In this study, the ACQ-7 ([Appendix 5](#)) will be used to assess improvements in asthma symptom control. The ACQ-7 ([Juniper 1999](#); [Juniper 2005](#) and [Juniper 2006](#)) is a seven-item disease-specific instrument developed and validated to assess asthma control in patients in clinical trials as well as in individuals in clinical practice. ACQ-7 will be provided to the site. All seven items are then scored on a 7-point Likert scale, with 0 indicating total control and 6 indicating no control. The questions are equally weighted and the total score is the mean of the seven items.

[figure not shown]
The proportion of patients who achieve an improvement of at least 0.5 in ACQ-7 (i.e. decrease of ACQ-7 score of at least 0.5 from baseline) at post-baseline visits will also be analyzed.

The ACQ-7 should be completed by the patient (first 6 questions) and investigator (for the last ACQ question – airway caliber FEV₁% predicted based on the equipment provided by spirometry vendor at the investigators site at Visits 101, 102, 202, 204, 207, 214 and EOT if applicable).

6.4.2.2 Asthma Quality of Life Questionnaire (AQLQ-S +12)

The AQLQ-S +12 is a 32-item disease specific questionnaire designed to measure functional impairments that are most important to patients with asthma ([Appendix 6](#)). It consists of 4 domains: symptoms, emotions, exposure to environmental stimuli and activity limitation. Patients are asked to recall their experiences during the previous 2 weeks and to score each item on a 7-point scale. The overall AQLQ score is the mean response to all 32 questions ([Juniper 1992](#), [Juniper 1993](#)). Clinically important differences in scores between any two assessments have been determined by the authors of the AQLQ. Changes in scores of 0.5 are considered clinically meaningful; changes of 1.0 are considered as moderate and > 1.5 as large changes for any individual domain or for the overall summary score ([Juniper 1994](#)).

AQLQ should be completed at Visits 102, 202, 204, 207, 210 and 214.

6.4.3 Electronic Diary

At Visit 1, all patients will be provided with an electronic diary (referred to as an e-Diary) to record rescue medication (salbutamol/albuterol) use and clinical symptoms, and from Visit 101 on, the PEF and compliance with the study treatment. The patients will be instructed to routinely complete the e-Diary twice daily – at the same time each morning and again approximately 12 hours later in the evening. The e-Diary is to be reviewed at each clinic visit until study completion. Sites and patients will receive appropriate training and guidance on the use of the e-Diary device. A list of the asthma control e-Diary questions is provided in [Appendix 8](#).

6.4.3.1 Peak Expiratory Flow (PEF)

An electronic Peak Flow Meter part of the e-diary device will be provided to each patient at Visit 1 for the measurement of morning and evening PEF during the run-in and treatment periods.

PEF will be measured at consistent times for a patient, in the morning and evening each day during the study from Visit 101 to 214. The measurements will be performed using an e-Peak Flow Meter provided to the patients at Visit 1. PEF will be measured twice a day; in the evening just prior to taking study medication and again 12 hours later and as soon as possible after waking in the morning. Patients should be encouraged to perform morning and evening PEF measurements BEFORE the use of any rescue medication. At each timepoint, the patient should be instructed to perform 3 consecutive maneuvers within 10 minutes. These PEF values are captured in the e-PEF/diary. The best of 3 values will be used.

6.4.3.2 Rescue Medication Usage

The use of rescue salbutamol/albuterol should be recorded by patients in their e-Diary twice each day in the morning and evening prior to taking study medication from Visit 1 until Visit 214. In the morning patients should record the number of puffs of rescue medication they have taken during the night and since the last diary entry, and in the evening patients should record the number of puffs of rescue medication they have taken during the day since the morning diary entry.

6.4.3.3 Investigational Medication Usage

In order to ensure compliance and safety follow-up, the patients will be requested to record once per week in the e-diary whether he/she missed any dosage in the morning or in the evening, and from which inhalation device from visit 201 to visit 214.

6.4.4 Worsening of asthma

Investigators and patients will be instructed how to deal with worsening of asthma symptoms. The data captured in the e-Diary will also be used to alert the patient and/or investigator to possible signs of worsening asthma and to possible asthma exacerbation. The investigator must provide the patient with written instructions to contact the investigator if at any time during the trial from the run-in onwards if one or more of the following criteria of worsening asthma develops:

Asthma Worsening Criteria alerts

- > 20% decrease in FEV₁ from baseline value (this criterion applies to Investigator review at the time of a study visit or possibly an alert setting if device structured to capture)
- > 50% increase in SABA use and > 8 puffs per day on 2 out of any 3 consecutive days compared to baseline
- ≥ 20% decrease in AM or PM PEF from baseline on 2 out of any 3 consecutive days compared to baseline
- < 60% of PEF compared to baseline
- Night time awakenings requiring SABA use on at least 2 out of any 3 consecutive nights

- Urgent unscheduled clinic visit due to asthma related deterioration

Note: The reference for the worsening of asthma during the run-in epoch would be the FEV₁ and PEF taken at Visit 101. The baseline FEV₁ for the treatment epoch is taken at treatment Day 1 (Visit 201). The baseline PEF (morning and evening) for the treatment epoch is calculated at visit 102 and is the mean of the best of the three daily PEF measurements over the past 14 days.

If any of the above criteria (including the alert from e-diary) are met while a patient is in the run-in or treatment epoch, the investigator should assess the patient condition. If this occurs during run-in epoch, and it is considered a clinically significant worsening in the investigator's opinion, the patient should be treated as appropriate and discontinued prior to randomization. Once the condition is resolved, if eligibility criteria are met, the patient may be reconsidered for rescreening.

The alerts which are triggered by above criteria are in place to detect early onset of asthma worsening at any time during the study to help direct early intervention. Therefore the investigator should do the following when alerts are received:

- Reviewing alert trends over time, in particular PEF decreases
- Call the patient promptly when any one specific alert type (e.g. PEF<60%) is received on consecutive days to further assess the clinical status. This may include urgent clinic visits as appropriate and/or immediate treatment.
- Implementing prompt treatment as necessary
- Reporting all type of events in the Asthma Exacerbation Episode CRF.

If patients believe their symptoms are worsening and/or receive alerts as outlined above, the patient should also notify the investigator and be evaluated by the investigator and treated as clinically appropriate.

Should there be any compliance issue on study drug or e-diary completion potentially putting the patient's safety at risk, please consider temporary or permanent discontinuation of study drug

Patients may also be withdrawn for any other safety reasons if, in the opinion of the investigators, it is appropriate to do so.

Worsening of asthma symptoms may require unscheduled evaluation between visits. Study site personnel must be available to monitor and document patient's progress until asthma control is regained.

6.4.5 Asthma Exacerbation

All type of asthma exacerbations meeting below criteria must be recorded in the Asthma Exacerbation Episode CRF (Asthma worsening as defined above should also be reported).

A **severe asthma** exacerbation (Draft note for guidance on clinical investigation of medicinal products for treatment of asthma CHMP/EWP/2922/01 Rev.1) is defined as an aggravation of asthma symptoms (like shortness of breath, cough, wheezing, or chest tightness) that requires systemic corticosteroids (SCS) for at least three consecutive days and/or a need for an ER visit, hospitalization due to asthma or death due to asthma.

- Start date and end date:

- In case of the use of SCSs for at least three days, the first day of treatment will determine the onset date of the event while the last day of treatment will define the stop date.

In the event that an ER visit and/or hospitalization due to asthma exacerbation were not associated with a course of SCSs as described above, start and end dates would be defined by the corresponding dates entered by the Investigator in the CRF.

A **moderate asthma** exacerbation in this protocol is defined as the occurrence of two or more of the following:

1. Progressive increase of at least one of the asthma symptoms like shortness of breath, cough, wheezing, or chest tightness. The symptoms should be outside the patient's usual range of day-to-day asthma and should last at least two consecutive days.
2. Increased use of "rescue" inhaled bronchodilators defined by:
 - > 50% increase in SABA use and > 8 puffs on 2 out of any 3 consecutive days compared to baseline captured

Or

- Night time awakenings requiring SABA use on at least 2 out of any 3 consecutive nights

3. Deterioration in lung function, which last for two days or more but usually not severe enough to warrant SCSs for more than 2 days or hospitalization. This deterioration would be defined by:

> 20% decrease in FEV₁ from baseline value

Or

≥ 20% decrease in am or pm PEF from baseline on 2 out of any 3 consecutive days compared to baseline.

Or

< 60% of PEF compared to baseline

- A **mild** asthma exacerbation is defined as the occurrence of one of the following criteria:

1. Deterioration of at least one asthma symptoms like shortness of breath, cough, wheezing or chest tightness.

2. Increased use of "rescue" inhaled bronchodilators

3. Deterioration in lung function, which last for two days or more but usually not severe enough to warrant SCSs or hospitalization.

This deterioration would be defined by:

> 20% decrease in FEV₁ from baseline value

Or

≥ 20% decrease in am or pm PEF from baseline on 2 out of any 3 consecutive days compared to baseline.

Or

< 60% of PEF compared to baseline

“Start and end dates” of each reported event in the CRF will be used to determine whether two consecutively reported events should be considered as separate events or as a prolonged.

If a second exacerbation is reported less than 7 days after the end date of a previous episode, then this will be assumed to be one continuous exacerbation with the start date taken from the first episode and the end date from the second or last episode. If two events are merged based on this “7 day rule”, the highest reported severity will be used to describe the overall severity of the prolonged event.

The treatment of asthma exacerbations including the initiation of systemic corticosteroids should be done according to investigator’s or treating physician’s medical judgement and should be in line with national and international recommendations. If systemic corticosteroids are required, a patient may return to the study after successfully completing a taper of approximately 7-10 days. If patients require significantly longer treatment periods or chronic administration, they must be discontinued from treatment.

6.4.6 Appropriateness of efficacy assessments

The efficacy assessments selected are standard for this indication/patient population.

6.5 Safety

The following safety assessments will be performed:

- Medical history and physical examination including oropharyngeal examination
- Vital signs
- Hematology, Blood chemistry, Urinalysis
- Evening plasma cortisol
- ECG
- Adverse events including asthma exacerbations and serious adverse events
- Pregnancy (female patients). Additional pregnancy testing might be performed if requested by local requirements.
- Serious asthma outcomes (asthma-related hospitalizations, intubations or deaths)

ECG and Laboratory assessments will be centralized.

6.5.1 Physical examination

A complete physical examination will include the examination of general appearance, skin, neck (including thyroid), eyes, ears, nose, throat, lungs, heart, abdomen, back, lymph nodes, extremities, vascular and neurological. If indicated based on medical history and/or symptoms, rectal, external genitalia, breast, and pelvic exams will be performed at Visits 101, 207, 214 or EOT (if applicable). An oropharyngeal examination will be performed at each clinic visit.

Information for all physical examinations must be included in the source documentation at the study site. Significant findings that are present prior to informed consent being granted must be included in the Relevant Medical History/Current Medical Conditions screen on the patient’s e-CRF. Significant findings made after informed consent (Visit 1) is given which meet the definition of an Adverse Event must be recorded on the Adverse Event screen of the patient’s e-CRF.

6.5.2 Vital signs

Systolic and diastolic blood pressure and radial pulse rate (over a 30 sec interval), performed in the sitting position, will be recorded at each scheduled clinic visits as detailed in [Table 6-2](#). (At visit 101, 102, 201, 202, 204, 207, 210, 214, or EOT (if applicable) vital sign should be measured directly after the ECG assessments).

6.5.3 Height and weight

Height in centimeters (cm) will be measured at Visit 101 for all patients and will be measured only in adolescents at visit 207, 214 or EOT if applicable. Body weight (to the nearest 0.1 kilogram [kg] in indoor clothing, but without shoes) will be measured at Visit 101, 207, 214 or EOT (if applicable). BMI will be calculated based on height and weight.

6.5.4 Laboratory evaluations

A central laboratory will be used for analysis of all specimens collected. Details on the collections, shipment of samples and reporting of results by the central laboratory are provided to investigators in the laboratory manual.

All patients with laboratory tests containing clinically significant abnormalities should be followed regularly until the values return to within the normal ranges or until a valid reason other than drug-related adverse experiences is identified, even after the medication has discontinued.

Safety Laboratory assessments (hematology, clinical chemistry, XXXXXXXXXX) will be performed at Visit 101, 201, 204, 207, 214 and EOT if applicable.

6.5.4.1 Hematology

Hemoglobin, hematocrit, red blood cell count, white blood cell count with differential, and platelet count will be measured.

6.5.4.2 Clinical chemistry

Albumin, alkaline phosphatase, AST (SGOT), ALT (SGPT), bilirubin, creatinine, γ -GT, glucose, potassium, magnesium, BUN and uric acid will be measured.

If the total bilirubin concentration is increased above 1.5 times the upper limit of normal range, total bilirubin should be differentiated into the direct and indirect reacting bilirubin.

6.5.4.3 Urinalysis

Dipstick measurements for specific gravity, pH, protein, glucose and blood will be performed at Visit 101, 201, 204, 207 and 214.

If the urine dipstick is abnormal, the sample will be sent to central laboratory for additional testing, including assessment of WBC and RBC sediments.

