Week – Start of Week	-4 to -2*	- 2	0	0	4	8	12	16	20	26	28	32	36	40	44	48	52			56
Day Number	-28 to -14*	-14	1	1/2	30	57	86	113	141	183/ 184	197	225	254	281	309	337	364/ 365 ⁶			395
Obtain Informed Consent and/or assent (including for sub-group)	X																			
Current medication review/ adjustment	X																			
Inclusion/ exclusion criteria	X	X	X																	
Randomization via IRT				S																
Medical History, Demography	X																			
History of Asthma exacerbation	X																			
Smoking history and status	X																			

Visit Number	1	101	102	201	202	203 ⁵	204	205 ⁵	206 ⁵	207	208 ⁵	209 ⁵	210	211 ⁵	212 ⁵	213 ⁵	214	EOT Early treatment discontinu ation	Early study discont inuatio n	301 ⁹
Epoch	Screen	Run-In		Treatment															PSW	Follow-up
Clinic (C) /Telephone (T)	C	C	C	C	C	T	C	T	T	C	T	T	C	T	T	T	C	C	T	T
Week – Start of Week	-4 to -2*	-2	0	0	4	8	12	16	20	26	28	32	36	40	44	48	52			56
Day Number	-28 to -14*	-14	1	1/2	30	57	86	113	141	183/ 184	197	225	254	281	309	337	364/ 365 ⁶			395
Run-in medication		X																		
Pregnancy test (serum) ¹		X															X	X		
Pregnancy test (urine) ¹	X		X							X										
Urine analysis (dipstick)		S		S			S			S							S	S		
Device training ⁴	S		S																	
Concomitant medication review	X	X	X	X	X	X	X	X	X	X	X	X	X	X	X	X	X			
Physical examination		S								S							S	S		
Oropharyngeal examination		S	S	S	S		S			S			S				S	S		
Record height (adult patients to record it ONLY at Visit 101) and weight		X								X							X	X		
ECG ²		X		X			X			X			X				X	X		

[figure not shown]
Visit Number	1	101	102	201	202	203 ⁵	204	205 ⁵	206 ⁵	207	208 ⁵	209 ⁵	210	211 ⁵	212 ⁵	213 ⁵	214	EOT Early treatment discontinu ation	Early study discont inuatio n	301 ⁹	
Epoch	Screen	Run-In		Treatment																PSW	Follow-up
Clinic (C) /Telephone (T)	C	C	C	C	C	T	C	T	T	C	T	T	C	T	T	T	C	C	T	T	
Week – Start of Week	-4 to -2*	-2	0	0	4	8	12	16	20	26	28	32	36	40	44	48	52			56	
Day Number	-28 to - 14*	-14	1	1/2	30	57	86	113	141	183/ 184	197	225	254	281	309	337	364/ 365 ⁶			395	
Vital signs ²		X	X	X	X		X			X			X				X	X			
Issue rescue medication as necessary	S	S		S	S		S			S			S								
Review rescue medication use		X	X	X	X		X			X			X				X	X			
Spirometry Practice (optional)	X																				
Screening spirometry			X																		
FEV ₁ reversibility test (SABA) ¹⁰		X																			
Spirometry ²				X	X		X			X							X	X			
Issue e-Diary ⁵	X																				

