Day Number	-28 to - 14*	-14	1	1/2	30	57	86	113	141	183/ 184	197	225	254	281	309	337	364/ 365 ⁶			395
AQLQ-S+12 ³			X		X		X			X			X				X			
Telephone patient 1 day in advance of visit				S	S		S			S			S				S			
Record healthcare visits for asthma worsening					X	X	X	X	X	X	X	X	X	X	X	X	X	X	X	

Visit early study discontinuation should be used for Premature study withdrawal (please refer to [Section 5.4.10](#) and [Section 5.4.11](#))

*: Time between Visit 1 and 101 can be adapted according to the required wash-out from previous medication listed in [Table 5-2](#)

S These assessments are source documentation only and will not be entered into the e-CRF

X assessment to be reported in the clinical database

¹ For females of child-bearing potential only unless surgically sterile. Additional pregnancy testing might be performed if requested by local requirements

█

³ All PROs assessed at Clinic should be completed before any other assessment. When a scheduled visit is planned on 2 consecutive days the PROs are to be completed on the first day.

⁴ Device training at Visit 1 is for e-diary/peak flow meter. Device training at Visit 102 is for Concept1, Twisthaler[®] and Accuhaler[®]. The diary is an electronic device and the questionnaires and other assessments are based on asthma symptoms

⁵ Site to call patient at specified timepoints in between clinic visits to check if patient asthma symptoms have worsened, any treatment required and e-diary completed accordingly. In case of an asthma exacerbation, the patient should be encouraged by the site to contact it for advice. If necessary, an unscheduled visit to the site may be organized and should capture AEs/SAEs, concomitant medication and safety laboratory exams as appropriate.

⁶ The last dose of study medication will be taken on day 365 in the morning (Visit 214)

■ [REDACTED]

⁹ Information about patients' survival will be obtained by a telephone call during the study treatment period and 30 days after the patient's last dose of study drug for completed patients. For patients who withdraw early, please refer to discontinuation of study treatment and premature patient withdrawal section

¹⁰ If reversibility fails on the first attempt as well as on the repeat, historical reversibility or bronchoprovocation would be acceptable as specified in [Section 4.1](#)

[REDACTED]

Table 6-2 Timed Assessment**

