Visit (Day)	Timepoint ¹	Spirometry (FEV ₁ , FVC) ⁴		Hematology Chemistry Urinalysis ⁵	Plasma cortisol	ECG ³	Vital sign ²	
Visit 201 (Day 1)	-45 min	X						
	-35 min					X		
	-25 min						X	
	-20 min			X ⁵	X ⁶			
	-15 min	X						
	0 min	Evening dosage						
	5 min	X						
	15 min	X						
	20 min						X	
	30 min	X		X				
	1 h	X				X	X	
Visit 201 (Day 2)	23h15 min	X						
	23h45 min	X						
	0 min	Evening dosage						
Visit 202 (Day 30)	-45 min	X						
	-30 min							
	-25 min							
	-15 min	X					X	
	0 min	Evening dosage						
	5 min	X						
	15 min							
	30 min	X						
	1 h	X						
Visit 204 (Day 86)	-45 min	X						
	-35 min					X		
	-25 min							
	-15 min	X		X ⁵			X	
	0 min	Evening dosage						
	5 min	X						
	15 min							
	30 min	X						
	55 min							
	1 h	X						
Visit 207 (Day 183)	-45 min	X						
	-35 min					X		
	-25 min						X	
	-20 min			X ⁵	X			
	-15 min	X						
	0 min	Evening dosage						

Visit (Day)	Timepoint ¹	Spirometry (FEV ₁ , FVC) ⁴		Hematology Chemistry Urinalysis ⁵	Plasma cortisol	ECG ³	Vital sign ²	
	5 min	X						
	30 min	X		X				
	1h	X				X		
Visit 207 (Day 184)	23hr15 min	X						
	23h45 min	X						
Visit 214 (Day 364)	-45 min	X						
	- 35 min					X		
	-25 min						X	
	- 20 min			X ⁵	X			
	-15 min	X						
	0 min		Evening dosage					
	5 min	X						
	20 min						X	
	30 min	X		X				
	1h	X				X	X	
Visit 214 (Day 365)	23h15 min	X						
	23h45 min	X		X	X			

¹ Study drug time doses. All study medication doses to be administered in the clinic. Time relates to the dose given from first device at visit unless otherwise specified

² Systolic and diastolic blood pressure and heart rate (radial pulse)

³ A minimum 3 min rest period from the beginning of ECG assessments to the start of spirometry manoeuvres must be observed at all times.

⁴ A minimum 10 min rest period from the end of spirometry maneuvers and the beginning of ECG assessments must be observed at all times. At all timepoints ECG should always be done first.

⁵ Urine analysis is to be done only if the urine dipstick is abnormal

⁶ It is baseline for the evening plasma cortisol

**Assessments are to be completed within a ± 5 mn window from Table 6-2 schedule

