2.7.3 Laboratory data

All laboratory samples will be processed through the central laboratory. Laboratory data consist of hematology, biochemistry and urinalysis measurements, including plasma cortisol. All data will be listed with abnormal values flagged.

Laboratory data measured more than 7 days after last inhalation of study drug are regarded as post-treatment data and will not be summarized, only listed. All data will be included in the analyses regardless of rescue medication use.

The following analyses will be performed by treatment:

- absolute values and change from baseline summarized for continuous laboratory parameters by visit and time point
- frequency table of results for categorical laboratory parameters by visit and time point
- shift tables relative to the normal reference ranges summarizing the change from baseline to most extreme post-baseline value for each continuous laboratory parameter
- shift tables from baseline to the worst post-baseline value for categorical laboratory parameters
- the number and percentage of patients with newly occurring or worsening laboratory abnormalities meeting the clinically notable criteria (see [Appendix 16.1.9](#) for definition of notable values) summarized by laboratory parameter, scheduled post-baseline visit and time point and additionally at any time on treatment considering all post-baseline data from scheduled, unscheduled and premature discontinuation visits

The by-visit/time point summaries will include the worst case post-baseline values (determined from all post-baseline data even if from unscheduled and premature discontinuation visits, if not measured more than 7 days after last dose). To determine the worst case, the direction of interest (maximum and/or minimum value) is tabulated for hematology and biochemistry

parameters in [Appendix 16.1.9](#). For continuous urinalysis parameters the direction of interest is always "High" (maximum value).

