For a patient to meet the criterion of a newly occurring clinically notable value, the patient needs to have a baseline value that is not clinically notable for that parameter. For a patient to meet the criterion of a worsening clinically notable value, the patient needs to have a baseline value that is clinically notable and also have a worse post-baseline value. For patients with missing baseline value, any post-baseline notable value will be considered as newly occurring. A listing of all patients with notable laboratory values will be provided.

The maximum change from baseline will be summarized for liver parameters (ALT, AST, alkaline phosphatase, total bilirubin).

Furthermore, the number and percentage of patients with newly occurring or worsening abnormalities in liver function tests (LFT) will be summarized by treatment and scheduled post-baseline visit and time point and additionally at any time on treatment considering all post-baseline data from scheduled, unscheduled and premature discontinuation visit (if not measured more than 7 days after last dose) based on the following criteria:

Notable liver function test values

Criterion
ALT > 3 x the upper limit of normal range (ULN) ALT > 5 x ULN ALT > 8 x ULN ALT > 10 x ULN ALT > 20 x ULN
ALT or AST > 3 x ULN ALT or AST > 5 x ULN ALT or AST > 8 x ULN ALT or AST > 10 x ULN ALT or AST > 20 x ULN
Total bilirubin > 1 x ULN Total bilirubin > 1.5 x ULN Total bilirubin > 2 x ULN Total bilirubin > 3 x ULN
ALP > 1.5 x ULN ALP > 2 x ULN ALP > 3 x ULN ALP > 5 x ULN
ALT or AST > 3 x ULN and total bilirubin > 1.5 x ULN ALT or AST > 3 x ULN and total bilirubin > 2 x ULN ALT or AST > 5 x ULN and total bilirubin > 2 x ULN ALT or AST > 8 x ULN and total bilirubin > 2 x ULN ALT or AST > 10 x ULN and total bilirubin > 2 x ULN ALT or AST > 20 x ULN and total bilirubin > 2 x ULN
ALP > 3 x ULN and total bilirubin > 2 x ULN ALP > 5 x ULN and total bilirubin > 2 x ULN
ALT or AST > 3 x ULN and Total Bilirubin > 2 x ULN and ALP < 2 x ULN (Hy's law)
ALT or AST > 3 x ULN and (nausea or vomiting or fatigue or general malaise or abdominal pain or (rash and eosinophilia))*

ALT = alanine aminotransferase, AST = aspartate aminotransferase, ALP = alkaline phosphatase

* Based on the signs/symptoms information as recorded on the liver events eCRF, not the adverse events eCRF.

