4) **Laboratory data** include hematology, biochemistry, urinalysis, and plasma cortisol. Baseline laboratory data is defined as the assessment taken 20 minutes pre-dose at Day 1. Checks will be performed to ensure the assessments were indeed taken prior to the first dose of study drug on Day 1. If this assessment is missing or not confirmed to be pre-dose, the last value taken at the run-in Visit 101 or at an unscheduled visit before the first administration of study drug will be used for baseline. Otherwise, the baseline laboratory data will be set to missing.

5) **Vital signs** include pulse rate and systolic and diastolic blood pressures. Baseline vital signs are defined as the assessment taken 25 minutes pre-dose at Day 1. Checks will be performed to ensure the assessments were indeed taken prior to the first dose of study drug on Day 1. If this assessment is missing or not confirmed to be pre-dose, the last value taken at the run-in Visit 101 or at an unscheduled visit before the first administration of study drug will be used for baseline.

6) Baseline **height and weight** are defined as the measurements taken at the run-in Visit 101. Missing baseline will not be imputed.

7) Baseline **ECG** is defined as ECG measured 35 minutes prior to the first dose of study drug on Day 1. Checks will be performed to ensure the ECG was indeed assessed prior to the first

dose of study drug. If it is missing (or not confirmed to be pre-dose), then the last assessment taken at the run-in Visit 101 or at an unscheduled visit before the first administration of study drug will be used. Otherwise, the ECG baseline will be set to missing without imputation.

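### Central urinalysis is done only after an abnormal dipstick, but the SAP summarizes it like a routine laboratory test: patients with normal pre-dose dipsticks have no central baseline, and no denominator is stated.

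*Protocol*

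**What the plan says.** **Who is tested.** Protocol 6.5.4.3: "Dipstick measurements for specific gravity, pH, protein, glucose and blood will be performed at Visit 101, 201, 204, 207 and 214". The central test follows only a positive screen: "If the urine dipstick is abnormal, the sample will be sent to central laboratory for additional testing, including assessment of WBC and RBC sediments". Footnote 5 of Table 6-2 agrees: "Urine analysis is to be done only if the urine dipstick is abnormal".

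**What is recorded.** In Table 6-1 the dipstick row carries the code S at each of these visits and at early treatment discontinuation. The legend explains S: "These assessments are source documentation only and will not be entered into the e-CRF".

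**What is analysed.** SAP 2.7.3 takes laboratory data from the central laboratory and names urinalysis as part of them. It plans by-visit values and changes, frequency tables for categorical parameters, and "shift tables from baseline to the worst post-baseline value for categorical laboratory parameters". It also sets the maximum as the worst case for continuous urinalysis parameters. The hematology and chemistry parameters listed in SAP 16.1.9.4 are numeric, so the categorical tables appear to be meant mainly for urinalysis.

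**Baseline.** SAP 16.1.9.3.2 includes urinalysis in its laboratory rule and takes the sample 20 minutes before the first dose. The fallback reads: "If this assessment is missing or not confirmed to be pre-dose, the last value taken at the run-in Visit 101", or an unscheduled pre-dose visit, is used instead. Otherwise baseline is missing. SAP 16.1.9.3.3 computes change only where both values exist.

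**The concern.** Whether a patient appears in a urinalysis table depends on the dipstick result. The SAP does not acknowledge this. It gives no denominator and no rule that a normal dipstick counts as a normal result. Its baseline rule treats a normal Day 1 dipstick in the same way as a lost sample.

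Urinalysis over 52 weeks is among the safety endpoints in Protocol 2.3 and SAP 2.1.3. The finding of most interest is a patient who is normal before dosing and abnormal later. The planned change and shift tables are least able to show that patient, and a reader could take the resulting tables as reassurance.

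**Working it through.** The documents state no figure for urinalysis, so there is none to reproduce. The first three steps follow from the text. The last two need assumed rates.

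**1. Normal before dosing, abnormal later.** The dipsticks at Visit 101 and Day 1 are normal, so no central sample is sent. Unless an unscheduled pre-dose result exists, baseline is missing. The later abnormal dipstick produces a central result, but there is no change from baseline and no baseline category for the shift table.

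**2. Abnormal at Visit 101, normal on Day 1.** Day 1 has no central value, so the fallback takes Visit 101. That value exists only because the Visit 101 dipstick was abnormal. The more recent normal finding is ignored.

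**3. By-visit means.** Each mean covers only patients whose dipstick was abnormal at that visit, so the group changes from visit to visit according to the result.

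**4. How many patients this could touch.** Assume 400 patients per arm (Protocol 9.8) and a probability q of an abnormal dipstick at each visit, with visits independent within a patient and no unscheduled samples.

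| q | Day 1 central results, 400q | Fallback baselines after a normal Day 1, 400q(1−q) | Share of those with a later result who have no baseline, (1−q)² | Day 1 result plus a result at one given later visit, 400q² |
|---|---|---|---|---|
| 5% | 20 | 19 | 90% | 1 |
| 10% | 40 | 36 | 81% | 4 |
| 20% | 80 | 64 | 64% | 16 |
| 30% | 120 | 84 | 49% | 36 |

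Independence is one extreme. If the same patients were abnormal at every visit, the third and fourth columns would fall to zero and the last would rise to 400q (20, 40, 80 and 120).

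**5. Frequency tables.** Let c be the probability that the central result is abnormal after an abnormal dipstick, and u the probability that it would have been abnormal after a normal dipstick.

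- True rate = q·c + (1−q)·u
- Rate among tested patients = c, whatever q is
- Rate over the full safety set, counting only observed abnormalities = q·c

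Example with assumed q = 10% versus 20%, c = 70% in both arms and u = 0:

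- Tested patients only: 28/40 = 70% versus 56/80 = 70%, difference 0.
- Full safety set: 28/400 = 7.0% versus 56/400 = 14.0%, difference 7.0 points. With u = 0 this is also the true difference.

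With u = 0 the tested-only percentage exceeds the true one by the factor 1/q: 20 at q = 5%, 10 at 10%, 5 at 20% and 3.3 at 30%. With u = 2% and c from 50% to 90%, the factor is about 3 to 14 over the same range of q. When q doubles between arms (5% to 10%, 10% to 20% or 15% to 30%), c is equal in both and u = 0, the hidden true difference runs from 2.5 points (c = 50%, lowest pair) to 13.5 points (c = 90%, highest pair).

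**The case against.** Testing a sample further only after a positive screen is ordinary practice, and the protocol sentence is not itself an error. Several stronger readings are tempting, and the documents do not support them.

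- **That abnormality rates are inflated as a matter of fact.** This needs patients with a result as the denominator. The SAP names none for these tables, and SAP 2.7 bases all safety evaluation on the safety set. Over that set the example keeps 7.0% versus 14.0%.
- **That a difference between arms necessarily disappears.** Exact cancellation requires the same c in both arms. A difference in c would still show. Even in the tested-only table the doubled counts (28 and 56) are visible, and all laboratory data are listed with abnormal values flagged.
- **That no normal-to-abnormal shift can be recorded.** A patient with an abnormal pre-dose dipstick and a normal central result has a normal baseline. The gap concerns patients whose dipsticks were normal.
- **That the SAP's missing-baseline rule for notable values makes matters worse.** The notable-criteria table in SAP 16.1.9.4 contains no urinalysis parameter, so that rule does not apply.
- **That the fallback biases the comparison between arms.** Both dipsticks precede dosing, so no imbalance is expected between randomized arms. Exclusion criterion 10 also removes clinically significant laboratory abnormalities at Visit 101. The fallback misclassifies baseline, which is a smaller matter.

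Other routes to a signal exist. Glucose, creatinine and BUN are measured in blood without this condition, and clinically significant abnormal results are adverse events under Protocol 7.1.

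Two places could be read against the point. Table 6-1 marks the safety laboratory row, including urinalysis, with X and no condition. In Table 6-2 the footnote mark stands on the column heading and the pre-dose cells but not on every later cell. Neither displaces the explicit condition in 6.5.4.3 and footnote 5, but the cross-references should be aligned.

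All these limits on size and scope stand. They do not supply a baseline for patients with normal dipsticks or a denominator for the tables.

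**Conclusion.** The point holds as a mismatch between conditional data collection and an analysis written for unconditional data. Three consequences follow whatever the denominator:

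- Patients with normal pre-dose dipsticks have no central baseline, so their shifts and changes are not captured.
- The Visit 101 fallback can override a normal Day 1 dipstick.
- Means describe a group selected on the result.

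A fourth is conditional. If patients with a result form the denominator, percentages are conditional on an abnormal dipstick and can mask a difference in how often dipsticks are abnormal.

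The size is unknown, because the documents give no dipstick or confirmation rates. The ranges above rest on assumed q of 5% to 30%, c of 50% to 90% and u of 0 to 2%. Only descriptive urinalysis tables are affected. Efficacy, type I error, power and the notable-value tables are not. The correction is worth making because urinalysis is a stated safety endpoint and the missing results are already in source.

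**What to change.** **Preferred.** Change the dipstick row of Protocol Table 6-1 from S to X, recorded as done, normal or abnormal. In SAP 2.7.3 and 16.1.9.3.2:

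- count a normal dipstick as a normal result at baseline and afterwards;
- use patients with a dipstick at the visit as the denominator;
- apply the Day 1 dipstick before any fallback to Visit 101.

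Also make the safety laboratory row of Table 6-1 refer to the dipstick condition. No new test or visit is needed. The cost is one short entry per scheduled dipstick: five visits for about 2000 patients gives up to 5 × 2000 = 10,000 entries, plus discontinuation visits, with some entered retrospectively if the change comes late.

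**If the e-CRF change is impractical,** amend the SAP alone:

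- state that central urinalysis is conditional on an abnormal dipstick;
- report the number tested and the number abnormal over the safety set N;
- do not apply the Visit 101 fallback to urinalysis;
- list these parameters without mean-change or shift tables.

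This costs only wording and removes the misleading summaries, but it does not recover the normal results.
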